5.1. Inclusion Criteria

Subjects will be eligible for inclusion in this study only if all of the following criteria apply:

1. Has completed participation of the 24-week double-blind treatment period in Study URO-901-3005 and demonstrated compliance with the study procedures and study medication schedule in the opinion of the investigator.
2. Is capable of giving written informed consent, which includes compliance with the requirements and restrictions listed in the consent form.
3. Has ability to continue to receive a stable dose of BPH treatment with either a) alpha blocker monotherapy or b) alpha blocker + 5-ARI.
4. In the opinion of the investigator, is able and willing to comply with the requirements of the protocol, including completing study questionnaires and the Bladder Diary.

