8.3.1. Vital Signs

Vital signs, including blood pressure, heart rate (by pulse), body temperature, and weight, will be assessed at the timepoints specified in the Schedule of Activities and Section 10.7 as follows:

- Blood pressure and pulse will be measured after the subject has been resting in a seated position for 5 minutes, after PRO assessments and before blood draws.
- Blood pressure measurements will be taken on the same arm and by the same site staff throughout the study, if possible.
- Sitting systolic and diastolic blood pressures will be determined by averaging 3 replicate measurements obtained approximately 1 to 2 minutes apart. The average of the 3 measurements will be used for eligibility and safety assessments.
- The same method for assessing temperature should be used at all visits for a particular subject.
- Body weight will be measured with subjects in street clothing with jacket/coat and shoes removed, using the same scale throughout the study, if possible.

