8.4.3. Follow-up of Adverse Events and Serious Adverse Events

After the initial AE or SAE report, the investigator is required to proactively follow each subject at subsequent visits/contacts. All AEs will be followed until approximately 21 days after the last dose of study drug. All SAEs will be followed until resolution, stabilization, the event is otherwise explained, or the subject is lost to follow-up (as defined in Section 7.3). If a subject dies during participation in the study or within 21 days of the last dose of study drug, the investigator will provide the Sponsor or designee with a copy of any postmortem findings including histopathology.

The investigator is obligated to perform or arrange for the conduct of supplemental measurements and/or evaluations as medically indicated or as requested by the Sponsor or designee to elucidate the nature and/or causality of the AE or SAE as fully as possible. This may include additional laboratory tests or investigations, histopathological examinations, or consultation with other health care professionals.

New or updated information will be recorded in the originally completed eCRF. As noted above, the investigator will submit any updated SAE data to the Sponsor or designee within 24 hours of receipt of the information.

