 - For subjects with systolic blood pressure < 140 mmHg and diastolic blood pressure < 90 mmHg at the Study URO-901-3005 baseline assessment, the average of 3 systolic blood pressures ≥ 140 mmHg or diastolic blood pressures ≥ 90 mmHg (or both) at any 2 consecutive visits after baseline
 - For subjects with systolic blood pressure ≥ 140 mmHg or diastolic blood pressure ≥ 90 mmHg at Study URO-901-3005 baseline, an increase compared to baseline at 2 consecutive visits in the average of 3 systolic blood pressures by ≥ 20 mmHg or 3 diastolic blood pressures by ≥ 10 mmHg
 - Initiation or increase in dose of medication for treatment of hypertension in any subject
- Adverse events consistent with orthostatic hypotension as confirmed by orthostatic vital signs

- Elevated serum aspartate aminotransferase (AST) or alanine aminotransferase (ALT) lab value requiring that study drug be temporarily withheld or permanently discontinued (see Section 8.4.6.1 and 8.4.6.2). To date, no concern regarding drug-induced liver toxicity has been identified; however, the Sponsor is monitoring laboratory data for a potential safety signal, consistent with Food and Drug Administration guidance [[FDA Guidance, 2009](#)].
- Neoplasms

Serious AESIs and elevated liver enzymes or bilirubin requiring withholding of study drug (see Section 8.4.6.1) must be reported within 24 hours of the study site personnel's knowledge of the event by marking the appropriate box on the AE eCRF and assigning the most appropriate category. Additional information should be provided as directed in the eCRF Completion Guidelines. AESIs that also meet the definition of an SAE must be reported as an SAE, as described in Section 8.4.4. Nonserious AESIs should be reported within 72 hours of the site personnel's knowledge, using the AE eCRF.

8.4.6.1. Criteria for Temporary Withholding of Study Treatment in Association with Liver Test Abnormalities

Elevated liver enzymes or bilirubin sufficient to require withholding study medication must be reported **within 24 hours of the study site personnel's knowledge of the event** using AESI specific eCRFs/forms/worksheets provided for the study.

Hepatic enzymes will be monitored in accordance with FDA drug-induced liver injury guidelines [[FDA, 2009](#)].

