10.7.2. Open-label Treatment Period, Visit 12 (Week 28 [Day 197 ± 4 days])

- Review AEs/SAEs
- Review concomitant medications
- Record blood pressure (3 results taken 1-2 minutes apart after sitting for 5 minutes), pulse, respiration, temperature, and weight
- Measure post-void residual volume
- Review and data enter completed Bladder Diary
- Dispense Bladder Diary
- Dispense open-label study drug

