3.1.2. Safety Analysis Set Extension

The Safety Analysis Set Extension (SAF-Ext) will serve as the primary population for the analysis of safety data in this trial.

The SAF-Ext consists of all randomized subjects in Study URO-901-3005 who

- a) have completed the 24-week treatment period in the Study URO-901-3005, and
- b) enrolled into the extension Study URO-901-3006 and received at least one dose of vibegron in this study.

Safety endpoints will be descriptively summarized for the entire Safety Analysis Set Extension. No imputation will be performed for missing safety data. Baseline will be established as the last observation prior to the first dose of vibegron. All safety data collected on or after the first exposure to vibegron within the combined experience of the patient on URO-901-3005 and

URO-901-3006 will be included in the safety analysis for URO-901-3006, and all analyses by visit will index visits from the first dose of vibegron on either study; subjects who received placebo in study URO-901-3005 will only contribute safety data up to Week 28.

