4.2.2. Reporting Conventions

General rules

In general, all collected safety data and any derived efficacy and PRO data will be presented in subject data listings for all enrolled subjects. This includes all data collected on the parent study, URO-901-3005, relevant to the definition of baseline and all data collected on URO-901-3005 after the first dose of vibegron, excluding assessments not repeated during 3006 (orthostatic vital signs, ECGs, urodynamics, and prostate volume measurement). Listings will be ordered by treatment group, subject number, and assessment week or event date. The treatment group presented in listings will be based on the actual treatment assignment in study URO-901-3005 (placebo as 28 Weeks Vibegron 75mg, vibegron 75mg as 52 weeks Vibegron 75mg), unless otherwise noted.

Summary tables will be provided for all subjects who sign informed consent for study URO-901-3006. Unless otherwise specified; all demographic and baseline data and safety data will be presented by treatment group and overall. Unless otherwise specified; all efficacy data will be presented by treatment group. In general, continuous variables will be summarized to indicate the population sample size (N), number of subjects with available data (n), arithmetic mean, SD, median, minimum, Q1, Q3 and maximum values. Categorical variables will be summarized by the population size (N), number of subjects with available data (n), number of subjects in each category, and the percentage of subjects in each category. Unless otherwise noted, the denominator to determine the percentage of subjects in each category will be based on the number of subjects with available data (n) in the analysis set of interest. Select ordinal data may be summarized using both descriptive statistics and counts and percentages of subjects in each category, as appropriate.

The data analyses will be conducted using the SAS[®] System (SAS Institute Inc., Cary, NC) version 9.4 or above. The eClinical Solutions standard operating procedures will be followed for the validation of all SAS programs and outputs.

Formats

Numeric data will be reported at the precision collected on the eCRF. The reported precision from non eCRF sources may be adjusted to a clinically interpretable number of decimal places.

Unscheduled Visits

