7.5. Vital Sign Assessments

Vital sign data including blood pressure, pulse rate, respiration rate, body temperature and weight will be collected at all study visits except for the Week 1, Week 16, and 44 telephone visits. Height will be measured at Screening only. Blood pressure will be measured in triplicate at each visit. The average of triplicates will be used for summary. For subjects in URO-901-3005 Study Part 1 at any visits with orthostatic blood pressure measurements: blood pressure (in triplicate) and pulse rate taken pre-dose in sitting position are equivalent to all other pre-dose vital sign values and will be used. Orthostatic and standing blood pressure measurements collected during Part 1 of URO-901-3005 will not be included in any summaries on URO-901-3006.

For all parameters, absolute values and change from baseline will be presented for scheduled visits using descriptive statistics for continuous variables. In addition, the maximum post-baseline change from baseline value and change from baseline to the end of treatment will be summarized for each of the vital signs.

To further investigate changes in SBP/DBP/pulse rate from baseline, the following tables will be prepared:

- Counts and percent of subjects in each group with at least a 5/10/15 CFB at 2 consecutive post-baseline visits and at Week 52 will be produced for all subjects, by pre-existing hypertension category (Yes/No) and by pre-existing hypertension category (Yes/No).
- Maximum post-baseline CFB (including 95% CI of Mean)

The line plot of mean (SE) of change from baseline in blood pressure and pulse rate over time will be prepared. A by-subject listing, sorted by subject identifier, will be presented including all vital sign results (scheduled or unscheduled).

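### The orthostatic hypotension AESI requires a confirming measurement that the extension does not schedule, so its count after Week 24 is a lower bound

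*Protocol*

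**What the plan says.** The AESI list in protocol 8.4.6 includes "Adverse events consistent with orthostatic hypotension as confirmed by orthostatic vital signs", and SAP 7.3 repeats the entry. Neither gives another route to confirmation or a list of preferred terms.

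The measurements planned for the extension are seated:

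- Protocol 8.3.1: "Blood pressure and pulse will be measured after the subject has been resting in a seated position for 5 minutes".
- Protocol 10.7.2 (Week 28), repeated for Weeks 36 and 52: "Record blood pressure (3 results taken 1-2 minutes apart after sitting for 5 minutes), pulse, respiration, temperature, and weight".
- The Schedule of Assessments (protocol 1.3) lists no standing or orthostatic reading. Week 44 is a telephone contact.

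The SAP acknowledges the gap. Section 4.2.2 describes the parent-study data carried into the listings as "excluding assessments not repeated during 3006 (orthostatic vital signs, ECGs, urodynamics, and prostate volume measurement". Section 7.5 adds: "Orthostatic and standing blood pressure measurements collected during Part 1 of URO-901-3005 will not be included in any summaries on URO-901-3006".

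Three other provisions matter. Inclusion criterion 3 requires every man to continue on "either a) alpha blocker monotherapy or b) alpha blocker + 5-ARI". SAP 3.1.2 brings in "All safety data collected on or after the first exposure to vibegron within the combined experience of the patient on URO-901-3005" as well as on 3006, so treatment-emergent events from the parent study count for men who were on vibegron there. Protocol 8.4.3 obliges the investigator to "perform or arrange for the conduct of supplemental measurements and/or evaluations as medically indicated" when following up an adverse event, without naming a standing reading.

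**The concern.** Long-term safety is the primary objective, and the AESI summaries are where a reader will look for orthostatic hypotension in men who all take an alpha-blocker. The category requires a measurement that is not part of any planned visit after entry. A man who reports dizziness on standing can be recorded as having an ordinary adverse event without ever having the reading that would place him in the category.

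Other AESIs in protocol 8.4.6 are better supported. Hypertension rests on blood pressure taken at every clinic visit, and urinary retention is backed by residual volume at every clinic visit. Retention and urinary tract infection each carry a note on what to record when the definition is not met. Orthostatic hypotension has neither a scheduled measurement nor such a note.

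The affected period is the one this study adds: all vibegron exposure for former-placebo men, and Weeks 24 to 52 for continuing men. A low count there could reflect few events or few confirmations, and the planned outputs would not separate the two. A nonserious event left outside the category also falls outside the 72-hour AESI reporting rule.

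**Working it through.** **Scheduled readings.** Vital signs at Visit 11 (Week 24) are the parent study's assessments and are not repeated (protocol 1.3 and 8.1). That leaves three clinic visits, at Weeks 28, 36 and 52. Standing readings scheduled: 0 of 3.

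**The plan's own figures.** The documents give no expected rate for this AESI. The only related figure is the sample size (protocol 9.7, SAP 1.2.4): about 300 men, about 33% dropout, 100 completing one year on vibegron. If half the men come from the parent vibegron arm, 300 × 0.5 × (1 − 0.33) = 100.5, which reproduces the 100. The half is an assumption, because the documents do not state the parent allocation.

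**What a zero count would show.** Let p be the true proportion of men with an event and s the average chance that a true case is confirmed. Confirmed events then occur at rate p × s. With 0 confirmed events in n men, the exact one-sided 95% upper limit is

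U = 1 − 0.05^(1/n) for p × s, and therefore U/s for p.

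- n = 300: U = 1 − 0.05^(1/300) = 0.99%.
- n = 100: U = 1 − 0.05^(1/100) = 2.95%.

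The documents give no value for s, so a range is shown. The last two columns use n = 300 and an assumed true rate of 2% over the extension: expected count = 300 × 0.02 × s, and chance of none = (1 − 0.02s)^300.

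| s (assumed) | Upper limit on true rate, 0/300 | Upper limit on true rate, 0/100 | Expected confirmed count | Chance of observing none |
|---|---|---|---|---|
| 1 | 0.99% | 2.95% | 6.0 | 0.2% |
| 0.5 | 2.0% | 5.9% | 3.0 | 4.9% |
| 0.25 | 4.0% | 11.8% | 1.5 | 22% |
| 0.1 | 9.9% | 29.5% | 0.6 | 55% |
| 0 | none | none | 0 | 100% |

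Any s below 1 gives under-counting. A count near zero needs s near 0.

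**Contribution from the parent study.** Suppose 150 men came from the parent vibegron arm (again assuming an equal split), with the same 2% rate and s between 0.5 and 1 there. They would add 150 × 0.02 × 0.5 = 1.5 to 150 × 0.02 × 1 = 3.0 events, even with s = 0 in the extension. This is on the high side: SAP 7.5 places the orthostatic readings in Part 1 of that study, whose size is not given, and the safety set contains only men who completed its 24 weeks.

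**The case against.** The strongest reply is that an AESI starts with an adverse event and is then confirmed, so it does not depend on routine screening. The follow-up duty in protocol 8.4.3 and the unscheduled visits allowed in 4.1 let a site take a standing reading for a symptomatic man. Sites assign the AESI category on the eCRF, and the SAP contains no rule that rejects an assigned AESI lacking a recorded reading. SAP 7.5 leaves parent-study blood pressure measurements out of summaries, but it does not remove an event already confirmed there. Unconfirmed events still appear by system organ class and preferred term, and the safety analysis is descriptive.

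All of this stands, and it rules out two stronger readings that a reader might infer. One is that a near-zero count is built into the design. The documents do not support that, because for-cause confirmation is possible and parent-study cases can enter for the 52-week group. The other is that a zero count would support no upper limit at all, which is true only if s is exactly 0.

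The reply does not close the gap. The follow-up duty is general, and confirmation rests on each site's initiative. A reading taken days after a transient episode may not confirm it, and between Weeks 36 and 52 the only planned contact is by telephone. Parent-study cases cover only the first 24 weeks of one group. In the general tables, related events may be spread over several preferred terms, with no planned grouping.

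**Conclusion.** The AESI definition and the vital-sign schedule do not match. The confirmed count after Week 24 is a lower bound whose capture probability is unknown. If none were seen in 300 men, the limit of about 1.0% would apply to confirmed events only; the limit for true events would be 2.0% at s = 0.5 and 4.0% at s = 0.25.

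These figures are illustrative. They assume 300 treated men, one average s across men and periods, and no allowance for dropout. Men in the 52-week group would in practice have a mixture of parent-study and extension values of s. The finding of under-ascertainment itself needs only that some true cases go unconfirmed.

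The effect is confined to the AESI category. Events recorded as adverse events are not lost from the safety data, and how readers would interpret a low count is a matter of inference. This is a modest defect that is cheap to correct.

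**What to change.** In SAP 7.3 and Tables 14.3.2.12, 14.3.2.13 and 14.3.2.20:

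1. Keep the confirmed AESI line as defined.
2. Add a second line for a preferred-term list fixed before database lock (for example orthostatic hypotension, postural dizziness, presyncope and syncope), counted regardless of confirmation. In the listing (14.3.2.20), include these records with a flag for confirmed cases.
3. Footnote that orthostatic vital signs were not scheduled in 3006, so the confirmed count is a lower bound.

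SAP 7.3 describes the two AESI summaries as by category, while SAP Table 9 titles them by preferred term. The layout should show the category row so that the two lines can be compared.

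The qualifier in protocol 8.4.6 and the vital-sign procedures in 8.3.1 should also be reconciled.

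The analysis change costs SAP text, a term list and some programming, with no added visit or test. The added line is less specific than the predefined AESI, and the confirmed line beside it makes that visible.

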8.4.7. Pregnancy Management and Reporting to the Sponsor

In the event that a partner of a male study subject becomes pregnant during the study, if the subject agrees, the subject's pregnant partner should be notified of the subject's study participation and be requested to sign a Release of Information form, permitting transfer of information regarding the pregnancy and outcome to the Sponsor. If the subject and the subject's partner agree, the investigator should notify the partner's primary care physician and provide details of the subject's participation in the study.

Partner pregnancies are to be reported to the Sponsor **within 24 hours of awareness** by the study site personnel, using the pregnancy reporting forms and information for safety event reporting in Section 10.3. The expected date of delivery or expected date of the end of the pregnancy, last menstruation, estimated conception date, pregnancy result, neonatal data, etc. should be included in this information, as available.

If the subject and partner agree, the investigator will follow the medical status of the mother, the pregnancy, as well as the outcome of the infant at birth, and will report the outcome to the Sponsor.

8.4.8. Medication Errors

Medication error refers to any unintended error in the dosing and/or administration of the study drug as per instructions in the protocol. Medication errors generally fall into 4 categories as follows:

- Wrong study drug
- Wrong dose (including dosing regimen, strength, form, concentration, amount)
- Wrong route of administration
- Wrong subject (ie, not administered to the intended subject)

Medication errors include occurrences of overdose and underdose of the study drug.

Overdose: Unintentional administration of a quantity of the study drug given per administration or per day that is above the maximum recommended dose according to the protocol. This also takes into account cumulative effects due to overdose (see Section 8.5 for treatment and reporting of overdose). For this study, any dose of vibegron of 3 or more tablets within a 24-hour window is an overdose. There is no known antidote for an overdose.

Underdose: No underdose is defined for this study.

8.5. Treatment of Overdose

In the event of an overdose (3 or more tablets of study drug within 24 hours), the investigator or treating physician should:

- Contact the Sponsor's designated Medical Monitor immediately
- Closely monitor the subject for any AEs, SAEs, and laboratory abnormalities
- Report all overdose events on the eCRF, whether or not the overdose is associated with an AE. If the overdose resulted in an AE or SAE, refer to Section 10.3 for reporting requirements.
- Document the quantity of the excess dose as well as the duration of the overdosing in the eCRF.

Decisions regarding dose interruptions or modifications will be made by the investigator in consultation with the Sponsor's designated Medical Monitor based on the clinical evaluation of the subject.

9. Statistical Considerations

This section contains a brief summary of the statistical analyses for this study; full details will be provided in the Statistical Analysis Plan (SAP).

9.1. Hypotheses

9.1.1 Primary Objective and Hypothesis

The primary study objective is to demonstrate long-term safety of vibegron 75 mg in men with BPH with symptoms of OAB. There is no formal statistical primary endpoint hypothesis. Descriptive statistics will be used to evaluate safety endpoints, including the incidence of treatment-emergent AEs (SOC and PT) by originally randomized treatment group and for vibegron treatment overall, including events during all vibegron exposure from both Study URO-901-3005 and URO-301-3006.

9.1.2 Secondary Objectives and Hypotheses

There are no formal statistical hypotheses for this trial. The secondary study objective is to demonstrate long-term efficacy of vibegron 75 mg in men with BPH with symptoms of OAB.

9.2. Analysis Endpoints

The description of the endpoints and study time points at which each is measured are described in Section 3 and Section 1.3, respectively.

